(1) Patients between ages of 40 and 85 who are scheduled for screening colonoscopy with the following gastroenterologists at UC Davis :

[name]
[name]
[name]
[name]
[name]
[name] [name]
[name]

Exclusion criteria:

The following patients will be excluded:

- (1) Age less than 40 and greater than 85
- (2) Prior history of colon adenomas (tubular adenoma, sessile serrated adenoma, tubulovillous or villous adenomas) and colon cancer
- (3) Patients with inflammatory bowel disease
- (4) Patients suspected to have colon cancer based on non-invasive tests such as stool tests for hemoglobin or DNA, or imaging finding suggestive of colon cancer (CT or barium enema).
- (5) Patients undergoing colonoscopy for evaluation of symptoms such as abdominal pain, rectal bleeding, diarrhea, constipation, etc., or patient with iron deficiency anemia suspected to be due to ongoing bleeding inside the colon
- (6) Patients with family history of hereditary polyposis syndromes such as Lynch syndrome, familial adenomatous polyposis etc., which are associated with an increased risk of colon cancer
- (7) Patients unable to consent
- (8) Pregnant patients
- (9) Incarcerated patients
- (10) Non-English speaking patients

Number of Subjects:

We plan on recruiting a total of 1374 subjects with 687 subjects randomized to each arm.

PROTOCOL TITLE: Use of a Distal Colonoscope Attachment to Increase Detection of Sessile Serrated Adenomas

Consent Process

Currently, the standard practice is to obtain informed consent prior to a colonoscopy. Some of the patients presenting for their colonoscopy are via open access, thus no colonoscopy specific clinic appointments are done before their actual procedure.

Patients that are identified as being eligible for the study will be contacted 3 weeks prior to their procedure (if possible) but no less than one week. They will be contacted by IRB- approved secured Mychart message via the electronic medical record or telephone by research personnel via IRB approved phone script to inform them of the study. Information regarding the procedure and goal of the study will be provided to allow for sufficient time prior to their procedure to consider participation. A copy of the consent form will also be sent to them via mychart or mail.

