Patients agreeing to participate in the study will sign the informed consent form on the day of the scheduled colonoscopy procedure. Patients will be able to ask the consenting physician any questions regarding the study prior to signing the consent form.

As part of routine practice, our endoscopists will discuss with the patients about the colonoscopy - including consent, medication/ history review and discussions about the risks/benefits of the procedure. This conversation typically occurs in a quiet and private section in the pre-op rooms about 30-60 minutes before the procedure. The written consent discussion specific to our study will also be done in this same area. There is usually adequate time prior to the procedure for both the consents to be done.

Please see attached Consent form (HRP-502). Non-English speakers will not be included in the study due to the practical difficulty with translating the study materials and consents. Patients that are unable to provide consent for themselves will not be included in the study.

HIPAA Authorization for Research

With the approval of HIPAA Waiver of Authorization (HRP-441), the study coordinator may identify potential subjects through the Electronic Medical Record (EMR). Following the identification of a patient as a potential subject, the study coordinator may inform the potential subjects of the study via secured communication (MyChart messages) or telephone with an IRB-approved phone script.

5) Study Timelines

Timeline for enrollment of subjects will be November 2018 – May 2020. Data will be obtained from all patient medical records on an ongoing basis and completed once their pathology report is finalized (sessile serrated adenoma vs tubular adenoma vs. non-adenomatous polyps). Primary data analysis will begin immediately once all patients

PROTOCOL TITLE: Use of a Distal Colonoscope Attachment to Increase Detection of Sessile Serrated Adenomas

have been enrolled, completed colonoscopy and all data collected. We anticipate that primary data analysis will be completed by June 2020. This will be a one-time participation during the date of their procedure only. Subjects will only be contacted by their endoscopist for communication of colonoscopy results per regular standard practice at UC Davis.

6) Study Endpoints

Primary Endpoint:

- Sessile Serrated Adenoma Detection Rate

Secondary Endpoints:

- Overall adenoma detection rate
- Proximal colon adenoma detection rate

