- Mean number of adenomas per colonoscopy
- Mean number of sessile serrated adenomas per colonoscopy
- Adenomas per positive colonoscopy
- Sessile serrated adenomas per positive colonoscopy
- Colonoscope withdrawal time
- Differences if quality of colon preparation
- Major complication rates (perforation, major bleeding causing transfusion)

7) Procedures Involved

Our proposed study is a randomized control trial in which patients are randomized in a single-blinded fashion into one of 2 study arms. One arm of subjects will undergo their screening colonoscopy without any colonoscope attachments (conventional). A second arm of subjects will undergo their screening colonoscopy with the Endocuff Vision attachment.

All methods (colonoscopy without any attachment and colonoscopy with Endocuff Vision attachment) are approved standard of care options, and are already in clinical use.

Data that will be reviewed as part of the study includes: age, gender, smoking status, alcohol consumption, body mass index (BMI), history of diabetes, quality of bowel prep, withdrawal time, the number of polyps, location of polyps removed, size of the polyps removed, and histopathology of the polyps. These are data points that are routinely collected and reported as part of regular care of patients. This data will be reviewed and entered into the REDCap database by medical students, residents or fellows. GI faculty members' role will be to obtain consent, perform procedures, and analysis of the de-identified data.

8) Data and/or Specimen Management and Confidentiality

Data will be accessed from patient records using an encrypted, password-protected computer at UC Davis Medical Center. The computer is stored in the GI office in PSSB building. This room is accessible by staff/faculty members of the UC Davis Gastroenterology department. Each study patient will be assigned a unique study number. Patient identifier, including patient name (First and Last) and medical record number (MRN) associated with the study number will be entered into password protected REDCap along with other aforementioned data. The principal investigators will not have access to the REDCap database, and research staff responsible for data entry will export de-identified data and distribute de-identified data to the investigators conducting data analysis.

As staff of UC Davis, each investigator will have completed HIPAA compliance training.

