The data collected will be analyzed using a one-way ANOVA. Using a baseline incidence of sessile serrated adenoma detection rate of 10%, and to detect an effect size of 50%, with a power of 0.809, we would need 687 subjects in each study arm. We therefore aimed to enroll 687 subjects into each arm (2 arms for a total of 1374 subjects) to ensure we have enough subjects in each arm to detect an effect if present.

9) Data and/or Specimen Banking

Linkage between patient identifiers(First Name, Last Name, and MRN) and study number including other data will be saved on the UC Davis REDcap database using an encrypted, password-protected computer at UC Davis Medical Center, division of Gastroenterology office located at [name] and Ticon I. Only study staff designated for data entry will have access to the REDCap database. Upon request, the de-identified data will be exported from the REDCap database and distributed to the investigators for analysis. De-identified data used for this study will not be banked for future use. At the completion of the study, all linkage between the patient identifiers and the study number will be destroyed.

10) Provisions to Monitor the Data to Ensure the Safety of Subjects

This research does not involve more than minimal risk to the subject.

The PI affirms to uphold the principle of the subject's right to protection against invasion of privacy. Throughout this study, a subject's source data will only be linked to the study database or documentation via a unique identification number. As permitted by all applicable laws and regulations, limited subject attributes, such as sex, age, or date of birth, and subject initials may be used to verify the subject and accuracy of subject's unique identification number.

11) Withdrawal of Subjects

Participation in the study is completely voluntary, thus patients can withdraw at any time during or after the procedure. Written consent will be obtained from all subjects.

Withdrawning from the procedure has no negative implication on their colon cancer screening and subsequent clinical care. If a subject desires to withdraw from the study, all information associated with the particular subject will be discarded immediately.

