A patient may also be withdrawn from the research at the discretion of the endoscopist or PI. The PI may withdraw a subject if there is a clinical suspicion for hereditary polyposis syndrome and/or new case of inflammatory bowel disease (IBD) based on the colonoscopy. Also, there are scenarios where the regular colonoscope is switched to a pediatric colonoscope. This occurs in patients with altered/ post-surgical anatomy, preventing completion of the procedure using a standard colonoscope. In these cases, subjects may be withdrawn from the study.

12) Risks to Subjects

The attachment device proposed in our study is currently FDA approved for use in colonoscopy. There is no added risk to participating subjects. There is an overall minimal risk to subjects and that risk is similar to any and all risks for conventional colonoscopy. Although we will make every effort to ensure that all patient health information remains confidential, there is the risk of loss of confidentiality.

PROTOCOL TITLE: Use of a Distal Colonoscope Attachment to Increase Detection of Sessile Serrated Adenomas

13) Potential Benefits to Subjects

Subjects may benefit from increased sessile serrated adenoma detection.

14) Multi-Site Research

Only UC Davis Medical Center Endoscopy suites will be involved in this study.

15) Community-Based Participatory Research

Not applicable

16) Sharing of Results with Subjects

Under current standard of practice, patients are contacted by the endoscopist either through the phone, mail, my chart or in person during a clinic visit to discuss endoscopic and pathology results. The results of the study will not be shared with subjects until the study has been completed and all of the data has been analyzed.

17) Prior Approvals

Not applicable

18) Provisions to Protect the Privacy Interests of Subjects

The only people that will have access to subject personal information are the principal investigators, sub-investigators and research personnel during the study period. All information collected (including age, gender, smoking status, alcohol consumption, BMI, diabetes status, withdrawal time, bowel prep quality, size, number and types of polyps removed, cecum intubation time and complications of procedure) will be de-identified.

19) Compensation for Research-Related Injury

No compensation will be provided.

20) Economic Burden to Subjects

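### Optional improvement: the only analysis the protocol names is an unadjusted one-way ANOVA, valid for SSADR but leaving the baseline data already collected unused

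*Protocol*

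**What the plan says.** The method stands in the analysis paragraph at the end of Protocol section 8 (Data and/or Specimen Management and Confidentiality): "The data collected will be analyzed using a one-way ANOVA". No covariate, effect measure or confidence interval is named there. The same paragraph takes a 10% baseline rate and states that "to detect an effect size of 50%, with a power of 0.809, we would need 687 subjects in each study arm".

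Section 6 (Study Endpoints) gives the primary endpoint as "Sessile Serrated Adenoma Detection Rate". Its secondary endpoints include "Colonoscope withdrawal time" and "Differences if quality of colon preparation".

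Section 7 (Procedures Involved) lists what is collected: "Data that will be reviewed as part of the study includes: age, gender, smoking status, alcohol consumption, body mass index (BMI), history of diabetes", followed by preparation quality, withdrawal time and polyp data. Section 18 gives a similar list: "All information collected (including age, gender, smoking status, alcohol consumption, BMI, diabetes status, withdrawal time, bowel prep quality". Neither list mentions the endoscopist, although section 4 limits enrolment to patients "scheduled for screening colonoscopy with the following gastroenterologists at UC Davis".

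**The concern.** A one-way ANOVA has one factor, here the arm. By naming it, the protocol does more than leave the method to a later plan: it settles on an unadjusted comparison. A statistical analysis plan that made an adjusted model the primary test would depart from that sentence.

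What is given up is precision. If age, gender, smoking or the endoscopist predict whether a serrated lesion is found, adjusting for them shrinks the standard error of the treatment effect at no cost in patients. The sample size aims for power close to 80% with no stated reserve, so even a small gain is useful. The covariates also need fixing in advance. Under section 7, the faculty who perform the procedures also analyse the de-identified data, so covariates chosen after the data are seen would be open to challenge.

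**Working it through.** **Inputs.** From section 8: control rate 10%, effect size 50%, 687 per arm, power 0.809. Assumed: the 50% is relative (10% vs 15%, a difference of 5 points), and alpha is 0.05 two-sided.

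**1. The plan's own figure.** Power at 687 per arm, 10% vs 15%:

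- Pooled: SE under the null = sqrt(2 × 0.125 × 0.875/687) = 0.01784; SE under the alternative = sqrt((0.09 + 0.1275)/687) = 0.01779. Power = Phi((0.05 − 1.96 × 0.01784)/0.01779) = 80.1%.
- Unpooled: Phi(0.05/0.01779 − 1.96) = 80.2%.
- Noncentral F: 80.2%. Arcsine: 80.4%.

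The pooled formula needs 686 per arm for 80% and 702 for 80.9%. The stated 0.809 is thus reproduced to within a point, and 687 to within 2.2%.

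**2. Is the ANOVA valid here?** Exact enumeration over all pairs of Binomial(687, p) counts:

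| True rates | ANOVA F rejects | Chi-square rejects |
|---|---|---|
| 10% vs 10% | 5.02% | 5.02% |
| 15% vs 15% | 4.99% | 4.99% |
| 10% vs 15% | 80.33% | 80.33% |

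The two tests behave identically. Nothing is lost by using ANOVA on a yes/no outcome at this size.

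**3. What adjustment could add.** Let R² be the share of outcome variance explained by baseline factors (assumed; the protocol gives no figure). Adjusted SE ≈ 0.01779 × sqrt(1 − R²); power = Phi(0.05/SE − 1.96); equivalent extra patients = 1374/(1 − R²) − 1374.

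| R² | SE | Power | Gain (points) | Patients |
|---|---|---|---|---|
| 0% | 0.01779 | 80.2% | 0 | 0 |
| 1% | 0.01770 | 80.6% | +0.4 | 14 |
| 2.5% | 0.01757 | 81.2% | +1.0 | 35 |
| 5% | 0.01734 | 82.2% | +2.0 | 72 |
| 8% | 0.01707 | 83.4% | about +3 | 119 |
| 10% | 0.01688 | 84.2% | about +4 | 153 |

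**4. Simulation of the proposed model.** There were 16,000 runs per setting with 687 per arm and marginal rates of 10% and 15%. Assumed: 8 endoscopists of equal volume, age normal, gender 50/50, smoking 20%. Logistic regression gave a standardised risk difference, compared with ANOVA in the same runs.

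| Endoscopist / covariate logit SD | R² | ANOVA | Adjusted, with endoscopist | Gain (points) | Gain, listed covariates only |
|---|---|---|---|---|---|
| 0 / 0 | 0% | 80.6% | 80.4% | −0.2 | −0.2 |
| 0.15 / 0.2 | 0.7% | 80.3% | 80.6% | +0.3 | +0.4 |
| 0.3 / 0.3 | 2.0% | 80.3% | 81.2% | +0.8 | +0.6 |
| 0.5 / 0.4 | 4.5% | 80.1% | 81.8% | +1.7 | +0.8 |
| 0.7 / 0.5 | 7.8% | 80.1% | 82.9% | +2.9 | +1.2 |

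Gains were computed before rounding. Their Monte Carlo standard errors are 0.11 to 0.20 points with endoscopist and 0.07 to 0.15 without. Type I error of the adjusted test at 10% vs 10% was 5.0% to 5.2% (standard error 0.17) in the four settings checked. The simulation agrees with step 3. In the two strongest settings, at least half of the gain comes from the endoscopist.

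**The case against.** The strongest reply is that nothing here is wrong. An unadjusted comparison in a randomised trial is legitimate, and step 2 shows that it costs no error control and no power relative to chi-square. Covariates and confidence intervals are commonly left to a statistical analysis plan, which may exist. The section 8 sentence names one method without excluding others, so a later plan could add an adjusted supportive model without contradicting it. Every figure for the gain rests on assumed inputs, and the factor that adds most in the stronger settings, the endoscopist, is in neither data list.

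Most of this stands, and it is why the point is optional. What it does not answer is that the protocol is not silent: it commits the collected data to a method with no place for covariates. Changing the primary test means changing that sentence.

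Three stronger readings might be inferred, and the document supports none of them:

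- **That no effect estimate is planned.** Section 2 already states the primary endpoint as a difference in detection rates, and section 3 reports the team's previous study as both arm rates with a p-value. Only the interval is unnamed, and a separate plan may supply it.
- **That ANOVA is a special problem for complications.** With 0 vs 0 events the F statistic is undefined, but so is chi-square, and the format of safety tables can be left to a separate plan.
- **That the endoscopist is not recorded.** Both lists are worded as inclusive, so it may be captured anyway.

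**Conclusion.** The point holds as a low-cost improvement. The named analysis is valid for SSADR, but it is unadjusted and makes no use of baseline data already being collected.

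The size of the benefit is uncertain. A range of 0 to 2 points of power applies only up to about 5% explained variance and is not a bound, since 8 to 10% would give about 3 to 4. With age, gender and smoking alone, four of the five simulated settings fall below 1 point and the strongest gives +1.2. If nothing predicts detection, the gain is zero or a loss of about 0.2 points.

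The conclusion assumes a two-sided alpha of 0.05, a relative reading of the 50% effect, and prognostic strengths that the protocol does not supply. A reader might infer that applying ANOVA to a yes/no endpoint makes the primary test invalid; the exact calculation rules that out at this sample size.

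**What to change.** Replace the ANOVA sentence in section 8 with a pre-specified model: logistic regression of SSADR on arm, age, gender and smoking, plus endoscopist if recorded. Report a standardised risk difference with 95% CI and test it two-sided at 0.05. Fix the covariate list and a pooling rule for low-volume endoscopists before any data are analysed. The choice of age, gender and smoking over the other listed baseline items (alcohol, BMI, diabetes) is a judgement, since the protocol gives no figures to rank them.

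Do not adjust for withdrawal time or preparation quality. Both are in the section 7 data list, but both are also endpoints in section 6.

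The cost is a little programming, possibly one REDCap field for the endoscopist, and about 0.2 points of power if the covariates predict nothing. If the sponsor prefers no adjustment, naming a chi-square test with a risk difference and 95% CI would change no primary test result.

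### The protocol's single ANOVA sentence, read literally, also covers major complications, where it gives no result if no event occurs and a too-low upper limit on harm if events are few

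*Protocol*

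**What the plan says.** The analysis paragraph of section 8 (Data and/or Specimen Management and Confidentiality) contains the protocol's only statement of method: "The data collected will be analyzed using a one-way ANOVA". It makes no exception by endpoint type. The rest of the paragraph is the sample size for the sessile serrated adenoma detection rate (SSADR).

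Section 6 (Study Endpoints) ends its list of secondary endpoints with "Major complication rates (perforation, major bleeding causing transfusion"). Section 18, on privacy, counts "cecum intubation time and complications of procedure" among the information collected, although the data list in section 7 does not name complications. Section 12 (Risks to Subjects) states in advance that "There is no added risk to participating subjects".

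The enrolment target under Number of Subjects is: "We plan on recruiting a total of 1374 subjects with 687 subjects randomized to each arm". The protocol gives no expected complication rate, no safety margin and no interval method.

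**The concern.** A complication is a yes/no event that is likely to occur in very few of 1374 screening patients. A one-way ANOVA on 0/1 data estimates its error variance from the observed events. With no events there is no variance and no test. With very few events the pooled variance is poorly estimated and tends to be too small, and the symmetric interval built on it stops too low on the side that matters for safety.

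Major complications are the only harm endpoint listed, and so the trial's own check on the risk statement in section 12. An analysis that returns nothing, or an upper limit that is too low, would be a weak basis for any closing statement on safety. Because the protocol states a method, and that method does not suit this endpoint, the point is not about detail left to a statistical analysis plan.

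**Working it through.** **Inputs.** From the protocol: n = 687 per arm, 1:1; control SSADR 10%; effect size 50%, read as a relative increase to 15%; power 0.809. Assumed, because not stated: two-sided alpha 0.05, and complication rates between 0.01% and 2% per arm.

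**1. The plan's own figure.** Two-proportion formula: n = [1.960·√(2·0.125·0.875) + z_power·√(0.10·0.90 + 0.15·0.85)]² / 0.05².
- Power 0.80: (0.9167 + 0.3925)² / 0.0025 = 686 per arm.
- Power 0.809: 702 per arm.
- At n = 687 the power is 0.801.

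The plan's statement ("with a power of 0.809, we would need 687 subjects in each study arm") reproduces to within 1 point of power and about 2% of n. Sample size is not at issue.

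**2. No events.** For a and b events, F = (n·d²/2)/v, with d = (b − a)/n and v = [a(1 − a/n) + b(1 − b/n)]/(2n − 2). With a = b = 0, F = 0/0. The chance of no event in either arm at a common rate r is (1 − r)^1374:

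| assumed r | P(no event) |
|---|---|
| 0.01% | 87% |
| 0.05% | 50% |
| 0.1% | 25% |
| 0.2% | 6% |

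The same data do carry a bound. The exact two-sided 95% upper limit for 0/687 is 1 − 0.025^(1/687) = 0.54%. The Newcombe score-based 95% interval for the difference is ±0.56 points.

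**3. Few events: the upper limit.** The ANOVA-based limit is d + t·√(2v/n). For 0 versus 1, d = 0.146 points and the standard error is 0.146 points, so the limit is 0.146 + 1.96·0.146 = 0.43 points. Newcombe gives 0.82 points.

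An exact sum over all event counts gives the chance that the upper limit falls below the true difference (nominal 2.5%). The 0 versus 0 outcome is counted as a zero-width interval at zero, and hence as a miss:

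| true rates (assumed) | ANOVA misses | of which 0 v 0 | with events | Newcombe misses |
|---|---|---|---|---|
| 0.05% v 0.2% | 25.3% | 17.9% | 7.4% | 0.01% |
| 0.1% v 0.2% | 13.5% | 12.7% | 0.8% | 0.1% |
| 0.1% v 0.3% | 12.7% | 6.4% | 6.3% | 0.4% |
| 0.1% v 0.5% | 4.9% | 1.6% | 3.3% | 0.5% |
| 0.2% v 0.5% | 5.0% | 0.8% | 4.2% | 0.7% |
| 0.5% v 1.0% | 3.5% | 0.0% | 3.5% | 1.8% |

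At 0.1% versus 0.2% nearly all the misses are the 0 versus 0 case. At 0.1% versus 0.3% about half occur with events present, so the fault is not confined to the degenerate case. It fades as events become more common.

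**4. The p-value.** For 4 versus 0: d = 0.00582, v = 0.002898, F = 4.02, p = 0.045. Barnard's exact test gives 0.047, Boschloo's 0.114 and Fisher's 0.124. For 5 versus 0: ANOVA 0.025, Barnard 0.026, Boschloo 0.056, Fisher 0.062. The exact type I error of the F-test at nominal 5% is 0.5% at a rate of 0.1%, 2.6% at 0.2%, at most 4.7% up to 1%, and peaks at 5.1% near 1.7%.

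**5. The primary endpoint.** For 69 versus 93 SSADR events, ANOVA and chi-square both give p = 0.0447.

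**The case against.** **Scope.** The ANOVA sentence opens a paragraph that otherwise concerns only SSADR, and may not have been written with complications in mind. That is a fair reading of intent, but the wording has no limit, and section 18 puts complications among the information collected. A later plan that follows the protocol would inherit the method.

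**The interval is not planned.** The protocol names a test, not an interval, and sets no safety margin. The miss rates therefore describe an interval that would follow naturally from the stated method, not one the authors promised. They also depend on assumed rates and on counting 0 versus 0 as a zero-width interval. This stands, and it limits the weight of the point.

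**The zero-event failure is visible.** An analyst would see that the test cannot run and would report 0 and 0. Probably so, but the analysis would then be improvised.

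**Stronger readings that a reader might infer.**
- That ANOVA overstates small splits, since 4 versus 0 gives 0.045 against Fisher's 0.124. This does not hold as an error-rate claim: Barnard's exact test agrees with ANOVA, the exact tests differ among themselves, and the F-test's size stays below 5% for rates up to 1%.
- That the trial can yield no valid bound on harm. This is true at most of ANOVA output. The counts by arm still allow an exact or score bound.
- That the investigators will take a null result as proof of the statement in section 12. That statement is a pre-study risk description resting on the device's approval. Nothing ties it to the complication comparison.

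**Conclusion.** The point holds in a narrow form. Taken literally, the only stated method covers a rare binary endpoint for which it gives no result when there are no events (50%, 25% or 6% chance at assumed rates of 0.05%, 0.1% or 0.2%). When events are few, an upper limit derived from it is too low: about 13% missed at 0.1% versus 0.2% or 0.3%, falling to 3.5% at 0.5% versus 1.0%. These sizes rest on assumed complication rates, two-sided 95% limits and 687 analysed per arm.

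The p-value for small splits is not inflated, and neither the primary comparison nor the sample size is affected. Only one secondary endpoint is touched, so this is a desirable improvement and not a condition for the trial's validity.

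**What to change.** Add one sentence to the analysis paragraph of section 8 that exempts major complications from the ANOVA. Report event counts by arm with exact (Clopper-Pearson) 95% confidence intervals, and a score or exact 95% interval for the difference between arms. State that few or no events, or a non-significant difference, is not evidence of equal safety.

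This needs no further data and no change in sample size. The small cost is a wider interval and a more modest safety statement.

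### Section 11 has a withdrawing subject's whole study record discarded, even after the result is known, and the protocol requires no count of such removals by arm

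*Protocol*

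**What the plan says.** Section 11 of the Protocol sets no time limit on leaving: "patients can withdraw at any time during or after the procedure". It then fixes what happens to the data: "If a subject desires to withdraw from the study, all information associated with the particular subject will be discarded immediately". Allocation, findings and complications are not exempted. The next paragraph of section 11 covers withdrawal by the endoscopist or PI and does not mention disposal of data, so the discard rule is worded only for a subject who chooses to leave.

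Five other sections bear on the point:

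- Section 5 treats a subject's data as complete only when the pathology report is final, which is after the procedure.
- Section 6 makes the SSA detection rate (SSADR) the primary endpoint and lists among the secondary endpoints "Major complication rates (perforation, major bleeding causing transfusion".
- Section 7, on the polyp, histology and baseline items, says: "These are data points that are routinely collected and reported as part of regular care of patients". Section 18 adds to the information collected "cecum intubation time and complications of procedure".
- Section 16 has subjects told their results as routine care, by several routes, including "in person during a clinic visit to discuss endoscopic and pathology results".
- Section 9 ends the period in which a record can be traced to a person: "At the completion of the study, all linkage between the patient identifiers and the study number will be destroyed".

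No section says whether withdrawn subjects are to be counted or reported.

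**The concern.** In a randomised comparison, subjects should be analysed in the arm to which they were allocated, and everyone randomised should be accounted for. A rule that erases a record on request, after the outcome may be known to both subject and study staff, works against both aims. The plainest case is a subject who has a perforation and then withdraws because of it: the rule removes the event that the complication endpoint exists to count.

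A statistical analysis plan cannot repair this. It can define populations and sensitivity analyses only on records that still exist. The issue is thus an instruction that the protocol itself gives, and not a detail left for later.

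**Working it through.** **1. The plan's own figure.** Section 8 gives 687 per arm, power 0.809, a baseline rate of 10% and an effect size of 50%. I read the effect as relative (10% versus 15%) and assume a two-sided alpha of 0.05; neither is stated.

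n per arm = [z(0.975)·√(2·p̄(1−p̄)) + z(power)·√(p₁(1−p₁)+p₂(1−p₂))]² / (p₂−p₁)²

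With p₁ = 0.10, p₂ = 0.15, p̄ = 0.125 and power 0.809, this gives 702. The power at 687 is 0.801. The stated figures reproduce closely and are not in dispute; they serve only as the base for what follows.

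**2. The order of events.** Under sections 5, 7 and 16 a subject is randomised and examined, pathology is finalised, and the result is communicated. Under section 11 withdrawal is open throughout and afterwards. A result or complication can therefore be on record when the discard rule is triggered. The opportunity ends when the linkage is destroyed (section 9), because a record can then no longer be matched to a person. The date of study completion is not given. Section 5 says only "We anticipate that primary data analysis will be completed by June 2020", so I put no length on this window.

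**3. Effect of one discarded record on SSADR.** Expected positives are 0.10 × 687 = 68.7, taken as 69, and 0.15 × 687 = 103.05, taken as 103.

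| Arm | Full | One positive discarded | One negative discarded |
|---|---|---|---|
| Conventional | 69/687 = 10.044% | 68/686 = 9.913% (−0.131 points) | 69/686 = 10.058% (+0.015) |
| Endocuff | 103/687 = 14.993% | 102/686 = 14.869% (−0.124 points) | 103/686 = 15.015% (+0.022) |

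The design difference is 34/687 = 4.95 points, so a handful of removals barely moves it.

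**4. Effect on the complication endpoint.** One event is 1/687 = 0.146 points of the arm's rate. The protocol gives no complication rate, so the relative effect can only be tabulated: one removed event is all of a count of one, half of a count of two, and a quarter of a count of four.

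**5. Effect on power.** No withdrawal rate is given. For assumed losses of 1%, 5% and 10% in each arm, 680, 653 and 618 per arm remain, and power falls from 0.801 to 0.797, 0.781 and 0.758.

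**The case against.** Several points on the other side have force.

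- **Counting is not forbidden.** A reader might infer that the final report could not show how many subjects were removed, or from which arm. The text does not go that far. A tally without identifiers is not clearly information about a particular subject, and one could be kept under procedures not shown. What stands is that the protocol does not require it.
- **Withdrawals may be few.** Participation is a single occasion, the data come from routine records, and staying in asks nothing more of the subject. The trial is single-blind, presumably on the subject's side since the endoscopist sees the device, so withdrawal prompted by knowing the arm is unlikely. Withdrawal prompted by a result or a complication is not excluded.
- **The clinical record presumably survives.** Section 7 describes most items as routine-care data, so what is lost is the study record. Allocation is not on that list, however, and the protocol gives no route for bringing a withdrawn subject's data back.
- **Privacy may be the intention.** Section 10 stresses protection of privacy in a minimal-risk study, and the consent form, which I have not seen, may promise deletion. This limits how much can be retained, but it does not stand in the way of a non-identifying count.

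A reader might also infer that the primary comparison is biased. Arithmetic can produce that: from 103/687 versus 69/687 (p = 0.006), removing 10 positives from the Endocuff arm alone gives p = 0.035, and removing 15 gives p = 0.078. Nothing in the protocol suggests one-sided loss on that scale, so these figures carry no weight in the conclusion.

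**Conclusion.** The concern holds as one of traceability and of completeness of the complication count. Section 11 permits a randomised subject's allocation, outcome and complications to leave the study record after they are known, and nothing in the protocol requires those removals to be counted by arm. That conclusion rests on the text alone.

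The likely effect on the primary result is small: 0.12 to 0.13 points per SSA-positive record and 0.01 to 0.02 points per negative one, given 687 per arm and the relative reading of the effect size. The total depends on a number of withdrawals that the protocol does not give. The complication endpoint is more exposed if events are few, which is plausible but not stated. No imbalance between arms is shown, and withdrawals made by the endoscopist or PI lie outside the discard rule. The wording should be changed, though the trial's main conclusion does not hang on it.

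**What to change.** Reword section 11 to say three things:

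1. After a subject withdraws, no new study data are collected.
2. Allocation, colonoscopy and pathology results, and complications obtained up to that point are kept de-identified and analysed in the randomised arm, as far as the consent form and ethics review allow.
3. In every case, including when data are deleted, a non-identifying count of withdrawals and of major complications is kept by arm and reported.

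If the sponsor prefers to keep deletion, the third item alone restores accountability at almost no privacy cost, but it does not secure an as-randomised analysis of SSADR.

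The cost is a paragraph of wording with ethics review, and matching text in the consent form if it now promises deletion. The real downside is that a withdrawing subject's data would no longer be deleted automatically. One gap remains: a subject who withdraws before pathology is final would be counted but would have no histology in the study record.
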